6.7 BASELINE, TIME WINDOWS AND CALCULATED VISITS

With regard to effectiveness and safety endpoints, the term “baseline” refers to the last observed measurement prior to administration of Spiolto Respimat. Observation on the same day as administration of Spiolto Respimat is "baseline".

Effectiveness analyses will be performed based on calculated visits as shown in Table 6.7: 1. If two or more data points of a patient fall into the same interval, the closest value to the planned day will be selected. If there are two observations which have the same difference in days to the planned day or if there are two observations on the same day, the first value will be used.

Table 6.7:1 Baseline, time windows and calculated visits

Week label	Planned days	Time window (actual days on treatment)	
		Start	End
Baseline	1	The last observed measurement prior to or on administration of Spiolto Respimat	
Week4	29	2	57
Week12	85	58	127
Week24	169	128	267
Week52	365	268	End of study

7. PLANNED ANALYSIS

For End-Of-Text (EoT) tables, the set of summary statistics is: N / Mean / SD / Min / Q1 / Median / Q3 / Max. For tables that are provided for endpoints with some extreme data, median, quartiles and percentiles should be preferred to mean, standard deviation, minimum and maximum.

Tabulations of frequencies for categorical data will include all possible categories and will display the number of observations in a category as well as the percentage (%) relative to the respective treatment group (unless otherwise specified, all patients in the respective patient set whether they have non-missing values or not). Percentages will be rounded to 2 decimal places. The category missing will be displayed only if there are actually missing values.

In addition, individual values on demographics, safety and effectiveness will be presented in subject data listings.

7.1 DEMOGRAPHIC AND OTHER BASELINE CHARACTERISTICS

Only descriptive statistics are planned for this section of the report.

7.2 CONCOMITANT DISEASES AND MEDICATION

Concomitant diseases will be coded by the latest version of Medical Dictionary for Regulatory Activities (MedDRA). Frequency of patients will be summarized by system organ class (SOC) and preferred term (PT).

Concomitant medication will be coded by latest version of “Nihon-iyakuhinshu”.

7.3 TREATMENT COMPLIANCE

Compliance data is not collected in this study

7.4 PRIMARY ENDPOINT(S)

The analysis of the primary endpoint is described in Section 7.8.1.

7.5 SECONDARY ENDPOINT(S)

The secondary endpoints will be used as stated in the NIS Protocol Section 9.7.3.

7.5.1 Key secondary endpoint(s)

This section is not applicable as no key secondary endpoint has been specified in the protocol.

7.5.2 (Other) Secondary endpoint(s)

This section is not applicable as no secondary endpoint has been specified in the protocol.

7.7 EXTENT OF EXPOSURE

Only descriptive statistics are planned for this section of the report.

7.8 SAFETY ANALYSIS

All safety analyses will be performed on the treated set.

7.8.1 Adverse events

Unless otherwise specified, the analyses of adverse events will be descriptive in nature. All analyses of AEs will be based on the number of patients with AEs and NOT on the number of AEs.

For further details on summarization of AE data, please refer to the guideline 'Analysis and Presentation of Adverse Event Data from Clinical Trials (1)

AE analyses will be carried out after integrating AE data from CRF and AE data from perceive system. In addition, AEs coded as “no adverse event” will not be included in the AE analyses.

The analysis of adverse events will be based on the concept of treatment emergent adverse events. That means that all adverse events occurring between first drug intakes till 21 days after last drug intake during observation period will be analysed. For details on the treatment definition, see Section 6.1.

An overall summary of adverse events will be presented.

The frequency of patients with AEs, ADRs, SAEs and SADR will be summarised by primary system organ class and preferred term. Patients with ‘priority survey items’ according to the drug’s Risk Management Plan will be summarised separately. The analysis of “priority survey items”, “Important identified risks”, “Important potential risks” will be conducted for AEs, ADRs.

It is created that table of patient with ADRs in each subgroup defined in Section 6.4. Not only the frequency but also the odds ratios are displayed.

In addition summaries for the time to onset of first episode for the ADRs will be tabulated, by duration (<= 4 week, 4 to <= 12 weeks, 12 to <=24 weeks, 24 to <=52 weeks, > 52), by primary system organ class and preferred term.

Adverse events leading to death and adverse events leading to discontinuation will be also summarised by treatment, primary system organ class and preferred term.

An ADR is defined as an AE for which either the investigator or the sponsor (or both) assess the causal relationship to Spiolto Respimat as “Yes”. A SAE is defined as an AE for which either the investigator or the sponsor (or both) assess the seriousness either as “Serious”.

The system organ classes will be sorted according to the standard sort order specified by EMA, preferred terms will be sorted by frequency (within system organ class).

The following AEs are detected on the basis of the Standardised MedDRA queries (SMQs) or Boehringer Ingelheim customised MedDRA query (BICMQ) (details are described in ADS plan).

Safety will be assessed by treatment exposure time adjusted incidence rate (n in 100 patient years) of ADRs.

Priority survey items

- Cardiovascular adverse events
- Anticholinergic-related adverse events
- Beta2 agonist-related events

Important identified risks

- Cardiac failure
- Atrial fibrillation and extra systoles
- Ileus, Angle closure glaucoma
- Anaphylaxis

Important potential risks

- Cardiac disorder (Myocardial ischaemia, Cardiac arrhythmia)

- Intubation and mortality related to asthma

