#### Safety:

Safety will be assessed with the incidence (n and % in treatment group) and treatment exposure time adjusted incidence rate (n in 100 patient years) of AEs in patients treated with Tio+Olo FDC (treatment emergent). Results will be stratified by different treatment types prior to baseline and age as a general risk factor.

- Adverse Drug Reactions (ADRs) (primary outcome) : related AEs as judged by the investigator or sponsor with a suspected causal relationship with the Tio+Olo FDC 5µg/5µg treatment
- AEs leading to death
- AEs leading to discontinuation of the Tio+Olo FDC 5µg/5µg treatment)
- Serious Adverse Events(SAEs)
- Priority survey items: Cardiovascular adverse events, Anticholinergic-related adverse events, Beta2 agonist-related adverse events

Section 11 covers how to assess and report AEs including the definitions.

Additional subgroup analyses/ safety outcomes might be included based on new information that could become available during the course of the study.

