## 9.7 DATA ANALYSIS

This is an observational study to collect real-world data (i.e., data under routine medical practice) on safety and effectiveness of Tio+Olo FDC 5µg/5µg treatment. Analyses are descriptive in nature, including confidence intervals. Due to the nature of the observational study, no confirmatory statistical testing is foreseen in this study. Subgroup analyses are also performed if sample size allows.

Per local regulation, any patient who meets one of the following criteria is treated as ineligible for all analyses:

- No safety observation was documented after registration.
- No required registration procedure was followed.
- No valid site contract was available.

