### 9.7.2 Analyses of Safety

The safety analysis will include all patients registered in the study and receiving the Tio+Olo FDC 5µg/5µg treatment except for patients who meet the ineligible criteria (see section 9.7). In general, safety analyses will be descriptive in nature, be based on BI standards, and focus on AEs related to the Tio+Olo FDC 5µg/5µg treatment.

AEs will be coded using the current version of the Medical Dictionary for Drug Regulatory Activities (MedDRA) and will be based on the concept of treatment emergent AEs. To this end, all AEs occurring between the initiation of Tio+Olo FDC 5µg/5µg prescribed at baseline visit and 21 days (inclusive) after the last administration will be considered 'treatment emergent'. An AE is considered to be an ADR if either the physician/investigator who has reported the AE or the sponsor assesses its causal relationship as 'related'.

The incidence (n and % in treatment group) and treatment exposure time adjusted incidence rate (n in 100 patient years) of AEs in patients treated with Tio-Olo FDC (treatment emergent including 21 days after discontinuation of Tio+Olo FDC medication) will be tabulated by MedDRA SOC and PT for overall and for subgroups based on the important baseline characteristics, if sample size allows (see 9.3.3)

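### The SAP names an exposure-adjusted rate for ADRs only and shows subgroups by ADR frequency and odds ratio, although the protocol plans AE rates overall and by subgroup and SAP section 4 declares no change

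*SAP*

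**What the plan says.** **Protocol.** Section 9.3.2 (Safety) assesses safety by the incidence and the exposure-adjusted rate of AEs on treatment, and adds: "Results will be stratified by different treatment types prior to baseline and age as a general risk factor". Section 9.7.2 repeats both measures for treatment-emergent AEs, which "will be tabulated by MedDRA SOC and PT for overall and for subgroups based on the important baseline characteristics, if sample size allows". Section 9.7 sets the general terms: "Subgroup analyses are also performed if sample size allows", and "Analyses are descriptive in nature, including confidence intervals". Section 9.1 makes ADR incidence and rate the primary outcome and ends follow-up once discontinuation is reported. Odds ratios appear nowhere in the protocol.

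**SAP.** Section 7.8.1 summarises AEs, ADRs, SAEs and serious ADRs by frequency. Its one statement on rates is: "Safety will be assessed by treatment exposure time adjusted incidence rate (n in 100 patient years) of ADRs". Its subgroup table covers patients with ADRs, and of that table it says: "Not only the frequency but also the odds ratios are displayed". Section 7.7 describes exposure. Section 7.8.1 also covers onset: "In addition summaries for the time to onset of first episode for the ADRs will be tabulated", by duration class, SOC and PT. Neither is planned by subgroup in the available text. Section 4 states that nothing has changed from the protocol's methods.

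**Sizing.** Protocol 9.5 supports N=1000 by the Wilson interval width for the proportion with serious cardiovascular events, starting from 2.6% in pooled trials. SAP 7.8.1 has SAEs by SOC and PT, and cardiovascular events as a priority survey item for AEs and ADRs. It names no output for serious cardiovascular events as a group.

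**The concern.** The protocol plans a rate for all AEs, overall and by subgroup. The SAP names one for ADRs, with no subgroup rate of any kind. Because section 4 declares no change, the report could omit planned output without anyone having recorded a decision to drop it.

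The subgroup part matters more for interpretation. A patient who stops early has less time in which an ADR can be observed. Subgroups defined by prior treatment or age may differ in persistence. If so, a frequency and a crude odds ratio combine the risk of a reaction with the length of treatment. Without person-years by subgroup, a reader cannot tell whether an odds ratio below 1 means fewer reactions or earlier stopping.

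A smaller matter is that the report need not contain the estimate whose precision was used to justify the study size, or could show it on a grouping that does not match the 2.6% benchmark.

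**Working it through.** **1. The protocol's own figures (section 9.5).** Inputs: p0 = 0.026, p1 = 0.052, two-sided alpha 0.05, power 98%.

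n = [1.960·√(0.026·0.974) + 2.054·√(0.052·0.948)]² / 0.026² = 872.3, so 873. This matches.

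Wilson 95% interval at n = 1000:
- 26 patients: 1.78% to 3.78%, width 2.00 points.
- 52 patients: 3.99% to 6.76%, width 2.77 points.

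Both stated widths (2.0% and 2.8%) reproduce.

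**2. Protocol and SAP side by side.**

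| Output | Protocol 9.3.2 / 9.7.2 | SAP 7.8.1 |
|---|---|---|
| AE rate, overall | planned | not named |
| AE rate, by subgroup | planned if size allows | not named |
| ADR rate, overall | primary outcome (9.1) | named |
| ADR results, by subgroup | incidence and rate | frequency and odds ratio |

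**3. How far an odds ratio can move through exposure alone.** Assumptions, none of them from the documents: a constant hazard h = 0.05 per year in both subgroups, and mean exposure t. The proportion with an ADR is p = 1 − exp(−h·t), so the odds are exp(h·t) − 1. The true rate ratio is 1.0 throughout.

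| Exposure, shorter v longer (years) | p, shorter v longer | Odds ratio | Odds ratio with 21 days added to both |
|---|---|---|---|
| 0.8 v 0.9 | 3.92% v 4.40% | 0.89 | 0.89 |
| 0.7 v 0.9 | 3.44% v 4.40% | 0.77 | 0.79 |
| 0.6 v 0.9 | 2.96% v 4.40% | 0.66 | 0.68 |

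For the last row, (e^0.030 − 1)/(e^0.045 − 1) = 0.03045/0.04603 = 0.66. It hardly depends on the hazard: 0.665 at h = 0.02 and 0.657 at h = 0.10. It also stays at 0.66 if the same means arise because 43% against 11% stop at 28 days and the rest are treated for a full year.

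**4. The reverse case.** Suppose all ADRs occur soon after the start, with equal risk in both subgroups. The odds ratio is then 1.0, but the rate ratio is 0.9/0.6 = 1.5. Here the rate misleads, so neither measure is enough alone.

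**5. As it would look in a table.** Two subgroups of 500, h = 0.05, full exposure in the denominator:
- Longer exposure: 500 × 4.40% = 22 patients in 450 person-years, 4.9 per 100 (exact Poisson 95% CI 3.1 to 7.4).
- Shorter exposure: 500 × 2.96% ≈ 15 patients in 300 person-years, 5.0 per 100 (2.8 to 8.3).
- Odds ratio (15/485)/(22/478) = 0.67 (0.34 to 1.31).

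**6. Person-years need a definition.** SAP 5.4 ends treatment duration at last intake, while SAP 6.1 counts events for 21 further days. A patient who stops on day 28 has 28 days of exposure but 49 days in which events count, a factor of 1.75. At 365 days it is 386/365 = 1.06. The choice matters most in subgroups with early stopping.

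**The case against.** The strongest reply is that the SAP sentence on ADR rates excludes nothing. The SAP says in its introduction that it elaborates the protocol, and section 4 says nothing has changed, so the AE rates of Protocol 9.7.2 may simply still apply. An ADR emphasis also has support there, since the safety analyses are to "focus on AEs related to the Tio+Olo FDC" treatment. The primary outcome is covered overall, and subgroup rates were always conditional on size. This stands in part. A reader might infer that the AE rates were withdrawn, but the text does not show that. It shows that they are not named.

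SAP section 6.4, which defines the subgroups, is not in the available text, and neither are the AE guideline and the analysis data set plan. They may specify more, and their absence is not a defect of the plan. Section 7.8.1 itself, however, says what the subgroup table displays.

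The study is descriptive, and Protocol 9.9 already lists loss to follow-up and channeling as limitations. The exposure gap above is assumed, a mild gap gives only 0.89, and the worked interval (0.34 to 1.31) would not be read as a difference. All of this is fair. A reader might infer that the subgroup odds ratios will be biased, but without persistence data one can say only that they could be.

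Finally, a reader might infer from the serious cardiovascular proportion that an endpoint was dropped or that the sample size is wrong. Neither holds: Protocol 9.3.2 does not list it as an outcome, and the sizing figures are correct.

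**Conclusion.** The point holds as a mismatch between protocol and SAP that should be resolved. The SAP does not name the AE rates overall or by subgroup, names no subgroup rate even for ADRs, and records no change. The overall ADR rate is retained, so the primary outcome is not at risk.

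The possible effect on interpretation is moderate. An odds ratio between 0.66 and 0.89 can arise with no difference in rate when mean exposure is 0.6 to 0.8 years against 0.9. This rests on an assumed constant, equal hazard and on assumed exposures, and it shows that divergence is possible, not that it is expected. Since early onset reverses the pattern, the conclusion is to show both measures, not to replace the odds ratio. The serious cardiovascular row is a suggestion only. Confidence is medium because parts of the specification were not available.

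**What to change.** 1. In the SAP 7.8.1 subgroup table, add person-years and the ADR rate per 100 patient-years with 95% CI beside the frequency and odds ratio. Do this for prior treatment type and age, and for other subgroups where size allows. State whether person-years include the 21-day post-treatment window. Add a sentence such as: *Where the odds ratio and the rates differ, neither is read alone; exposure duration and time to first ADR in that subgroup are considered.*
2. Produce the Protocol 9.7.2 AE rates, overall and by subgroup where size allows, or record their restriction to ADRs in SAP section 4.
3. As an addition, report patients with serious cardiovascular events (n, %, 95% Wilson CI), using and naming the grouping behind the 2.6% benchmark. Summing PT rows of the SAE table would not give this, because one patient can have several PTs.

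The cost is a few table columns, one row and one sentence, all from data already collected; if the AE rates are kept, they add rate columns to the AE tables. Rate intervals will be wide in small subgroups, so the protocol's sample-size condition should stay.

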## **8. RESEARCH QUESTION AND OBJECTIVES**

This PMS study is one of the action plans of collecting post-marketing safety information focused on the following risks and information of Tio+Olo FDC 5µg/5µg in the J-RMP.

- Important identified risks: Cardiac failure, atrial fibrillation and extrasystoles, Ileus, Angle closure glaucoma, Anaphylaxis
- Important potential risks: Cardiac disorder (Myocardial ischaemia, Cardiac arrhythmia), Intubation and mortality related to asthma
- Important missing information: none specified

The study objective is to assess the long-term safety and effectiveness of Tio+Olo FDC 5µg/5µg in patients with chronic obstructive pulmonary disease (chronic bronchitis, emphysema) in real-world setting.

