## **9. RESEARCH METHODS**

### **9.1 STUDY DESIGN**

This is an observational study based on newly collect real-world data (i.e., data under real-world practice) to evaluate safety and effectiveness of Tio+Olo FDC 5µg/5µg in patients with chronic obstructive pulmonary disease (chronic bronchitis, emphysema).

The study will be initiated after marketing of Tio+Olo FDC 5µg/5µg in Japan. The study will consist of a baseline visit and further visits in a 52-week follow-up for patients who have initiated the Tio+Olo FDC 5µg/5µg treatment.

As this is an observational study, no specific treatment is mandated or withheld from the patients. The choice of maintenance treatment for chronic obstructive pulmonary disease (chronic bronchitis, emphysema) must be according to regular medical practice and at discretion of physician (i.e., no randomised assignment of patient to treatment [Tio+Olo FDC or other treatment] is performed). In total, approximately 1100 patients are planned to be registered at approximately 200 study sites in the study.

Patients participating in the subsequent follow-up will undergo regular observations. These observations should be reported after 4, 12, 24 and 52 weeks since the initiation of Tio+Olo FDC 5µg/5µg as long as they continue to receive the treatment. Patients will not be followed any longer once they are reported to have discontinued the Tio+Olo FDC 5µg/5µg treatment. Patients who experience adverse events will be followed up until detailed information on the outcome of the adverse event is collected.

The primary outcome of this study is the incidence and exposure-time adjusted incidence rate of adverse drug reactions (ADRs).

The secondary outcome of this study is:

- COPD assessment test (CAT) at 12 weeks.

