 - ICS+LAMA+LABA (free combination + fixed dose combination): Yes, No
 - Other respiratory medication
 - Theophylline: Yes, No
 - Mucolytic: Yes, No
- Previous therapy: Yes, No, Unknown

- Concomitant therapy: Yes, No, Unknown

Treatment exposure:

- Duration of Spiolto Respimat treatment [days] = (date of last treatment intake) - (date of first intake) + 1
If after the data lock, Spiolto Respimat is ongoing and date of last treatment intake is missing: date of last treatment intake = Latest date in book
- Duration of Spiolto Respimat treatment class [weeks]: <= 4 weeks, 4 to <= 12 weeks, 12 to <=24 weeks, 24 to <=52 weeks, > 52 weeks.
Note: In terms of days <= 29days, 29 to <= 85days, 85 to <= 169, 169 to <= 365, >365

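### The table of first ADRs by onset period has no person-time, so it mixes ADR risk with period length and attrition and cannot show whether risk changes with long-term use

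*SAP*

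**What the plan says.** The aim concerns long-term use. Protocol 8: "The study objective is to assess the long-term safety and effectiveness of Tio+Olo FDC".

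SAP 7.8.1 plans a table of first ADR episodes by time since start of treatment, by system organ class and preferred term: "summaries for the time to onset of first episode for the ADRs will be tabulated, by duration". The classes are "<= 4 week, 4 to <= 12 weeks, 12 to <=24 weeks, 24 to <=52 weeks, > 52". SAP 5.4 uses the same week limits for treatment duration and gives them in days: "In terms of days <= 29days, 29 to <= 85days, 85 to <= 169, 169 to <= 365, >365".

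The counting unit is the patient: "All analyses of AEs will be based on the number of patients with AEs and NOT on the number of AEs" (SAP 7.8.1). The sentence on the onset table names no denominator. The general rule in SAP 7 for percentages is "unless otherwise specified, all patients in the respective patient set whether they have non-missing values or not".

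On follow-up, Protocol 9.1 states: "Patients will not be followed any longer once they are reported to have discontinued". AEs count as treatment-emergent up to 21 days after the last intake (Protocol 9.7.2, SAP 7.8.1).

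An exposure-adjusted rate per 100 patient-years is planned: for ADRs in SAP 7.8.1, and in Protocol 9.7.2 by system organ class and preferred term, overall and by subgroup. The text available does not ask for it by onset period. It also plans no number at risk, no patient-years per period and no Kaplan-Meier estimate.

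**The concern.** A count of first ADRs in an onset period depends on three things: the risk per unit time, the length of the period, and the number of patients still observed and still free of an ADR. Here the second and third both vary. Period length grows about sevenfold from the first class to the fourth. The group at risk shrinks as patients stop treatment or have their first ADR, yet the default denominator stays at the full set.

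A single rate over the whole of follow-up averages across treatment time, so it cannot fill the gap. At stake is the reading of the long-term safety objective. The onset table is the output in the available text to which a reader would turn to ask whether ADRs become more or less frequent as treatment continues, and it would not answer that question.

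**Working it through.** **Plan's own figure.** None is given for this table, so there is nothing to reproduce. The check asks what the table would show under a known risk.

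**Inputs from the documents.** 1000 patients in the safety set (Protocol 9.5). Period limits at 4, 12, 24 and 52 weeks (SAP 7.8.1), so lengths of 4, 8, 12 and 28 weeks. Follow-up ends at discontinuation (Protocol 9.1).

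**Assumptions.** The documents give neither an ADR rate nor a discontinuation rate. I take a first-ADR hazard h = 0.10 per year and a proportion D discontinuing by week 52 of 20%, 35% or 50%, exponential and independent of ADRs. The 21-day tail and the class over 52 weeks are left out.

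**Formula.** With d = -ln(1-D), the expected number of patients with a first ADR between times a and b (years) is

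1000 × h/(h+d) × [exp(-(h+d)a) - exp(-(h+d)b)].

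For D = 35%, d = 0.4308 and h/(h+d) = 0.1/0.5308 = 0.1884.
- Weeks 0-4: 188.4 × (1 - 0.9600) = 7.5.
- Weeks 24-52: 188.4 × (0.7827 - 0.5881) = 36.7.

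**Constant risk: first-ADR patients per period**

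| D | 0-4 wk | 4-12 wk | 12-24 wk | 24-52 wk | Fourth/first, count | Fourth/first, per week |
|---|---|---|---|---|---|---|
| 20% | 7.6 | 14.6 | 20.6 | 42.6 | 5.6 | 80% |
| 35% | 7.5 | 14.2 | 19.2 | 36.7 | 4.9 | 69% |
| 50% | 7.5 | 13.6 | 17.6 | 30.4 | 4.1 | 58% |

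The per-week column divides the counts by 28 and by 4 weeks. As the denominator is 1000 throughout, percentages of all patients rise by the same factors as the counts. At D = 35% about 783 patients are still at risk at week 24.

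**Dividing by person-time.** At D = 35% the patient-years at risk in the four periods are 75.4, 141.8, 192.2 and 366.6. Dividing the unrounded counts by these returns 10.0 per 100 patient-years in each period, which is the true rate.

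**Rising risk.** If the hazard is 0.15 after week 24, the fourth period holds 54.3 patients at D = 35% and 45.0 at D = 50%. Per week that is 54.3/28 = 1.94 against 1.88 in weeks 0-4, and 45.0/28 = 1.61 against 1.87. A true 50% rise then looks flat or falling to a reader who allows for period length only.

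**Second check with the SAP's day limits.** The limits 29, 85, 169 and 365 days give lengths of 29, 56, 84 and 196 days. With a constant 5.13 per 100 patient-years (5% first-ADR risk over 365 days without discontinuation) and 30% discontinuation, the shares of all 1000 patients are 0.40%, 0.74%, 1.02% and 2.05%. In the opposite direction, equal shares of 1.25% in each period at 30% discontinuation correspond to rates of 16.1, 8.8, 6.4 and 3.2 per 100 patient-years. A five-fold fall would appear as a flat row.

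**The case against.** - **Direction of error.** A reader might infer that the table will make ADRs appear to fade. The documents do not support that. No per-week figure is planned, and under constant risk the tabulated counts rise. The apparent fall needs an extra division by period length. The error can go either way.
- **Denominator.** It comes from a general default, not from the onset-table sentence, and SAP 7.8.1 refers to an in-house AE guideline that is not supplied and could differ. This stands as a caveat. The count itself has the same defect whatever percentage is shown.
- **Other outputs.** Section 6.4 is cited in SAP 7.8.1 but is not in the text supplied, and the contents list also skips 7.6. It would go too far to say that nothing else in the full plan looks at time. The point is limited to the text available.
- **Partial context.** Treatment-duration classes with the same limits (SAP 5.4) and descriptive exposure statistics (SAP 7.7) would let a reader approximate how many patients remained on treatment at each limit. They give neither the number free of a first ADR nor the patient-years per period.
- **Over 52 weeks.** A reader might assume that almost nobody is at risk in this class. That is not established. It starts after day 365, which is the planned week-52 day in SAP 6.7; the week-52 window runs to the end of study, and the 21-day tail adds time.
- **Scope.** The study is descriptive, the primary outcome is incidence and exposure-adjusted rate, and no objective asks about change in hazard. Protocol 9.9 already lists loss to follow-up as a limitation. This limits the weight of the point, but Protocol 9.9 also asks that such limitations be taken into account in the analysis.
- **Yield.** With about 7.5 and 54 events, the standard error of the log rate ratio is sqrt(1/7.5 + 1/54) = 0.39. A true ratio of 1.5 would have a 95% interval of about 0.70 to 3.2. Period rates would describe the pattern and not prove a change.

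**Conclusion.** The point holds as a shortcoming of presentation and analysis. As specified in the text available, the onset table cannot separate ADR risk from period length and attrition, so it cannot inform the long-term question. The size depends on the assumed rates: over 20% to 50% discontinuation, a flat risk gives a 5.6- to 4.1-fold rise in counts and a drop to 80% to 58% per week. Other discontinuation patterns, or discontinuation related to ADRs, would change these numbers. Unequal period length alone is enough to break the link between count and risk.

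The effect is on interpretation only. The primary incidence, the overall exposure-adjusted rate and the sample size are untouched. A reader might infer that the study's ADR results are biased; nothing here supports that.

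**What to change.** In SAP 7.8.1, for each onset period, add:

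1. the number of patients under observation and free of a first ADR at the start of the period;
2. the patient-years at risk within it;
3. first ADRs per 100 patient-years with a 95% confidence interval.

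Do this for any ADR and, where counts allow, for the priority survey items. Show the class over 52 weeks only with its patient-years, or merge it with the last period. State the denominator of any percentage in the table, and whether the 21-day tail counts as time at risk, so that events and person-time match. Say that the rates are descriptive and not a test of change over time.

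The cost is SAP wording and one extra derivation from treatment and AE dates that are already collected. The downside is wide intervals in sparse periods.
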